2.2. Secondary Objectives

- Mean change in MMP-9 from baseline at week 1, week 2, week 4, week 8 and week 12 as measured by InflammaDry
- Mean change in tear break-up time (TBUT) from baseline at week 1, week 2, week 4, week 8 and week 12
- Mean change in conjunctival injection from baseline at week 1, week 2, week 4, week 8 and week 12 as measured on a scale of 0-4 and graded by the physician
- Change from baseline in meibomian gland scores (expressibility and quality) at week 1, week 2, week 4, week 8 and week 12.
- Mean change in tear osmolarity from baseline at week 1, week 2, week 4, week 8 and week 12 as measured by Tear Lab
- Mean change in DEQ-5 from baseline at week 1, week 2, week 4, week 8 and week 12
- Mean change in Best-corrected Visual Acuity (BCVA) from baseline at week 1, week 2, week 4, week 8 and week 12 as measured by ETDRS chart
- Mean change in Schirmer's score from baseline at week 1, week 2, week 4, week 8 and week 12 as measured by Schirmer's test strip

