4.1.2. Exclusion Criteria

A patient who meets any of the following criteria will be excluded from the study:

- Patients under the age of 18.
- Pregnancy (must be ruled out in women of child-bearing age with pregnancy test)

- Active infectious systemic disease
- Active infectious ocular or extraocular disease
- Altered nasolacrimal flow of either acquired, induced, or congenital origin
- Hypersensitivity to dexamethasone
- Patients who have been on topical immunomodulating agents in the previous 3 months to their baseline visit
- Patient being treated with either topical, oral, or intravenous immunosuppressive agents, immunomodulating agents, or steroid (including NSAIDS)
- Patients with severe disease that warrants critical attention, deemed unsafe for the study by the investigator

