4.3. Concomitant Medications and Procedures

At the discretion of their physician, patients may continue to receive all medications and standard treatments administered for other conditions.

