5.1.1. Study Procedures

Screening/Prescription

After the patient has provided informed consent, the following information will be collected:

- Inclusion/exclusion
- Demographics
- Medical history and concurrent illnesses
- Concomitant medications
- UCVA and MR/BCVA as measured by ETDRS chart at 4m
- Ophthalmic Examination with dilation
- Intraocular pressure
- Meibomian gland assessment (expressibility and quality)
- DED Assessment
 - Schirmer's
 - MMP9
 - Osmolarity
 - Conjunctival injection
 - TBUT
 - Ocular surface staining (sodium fluorescein and lissamine green)
- Subject reported AE's
- Restasis BID OU prescription
- Lotemax BID OU for 1 month prescription
- DEXTENZA® insertion in one eye

- Insert Visualization
- Physician ease of insertion questionnaire
- DEQ-5 

Week 1, Week 2, Week 4 and Week 8

- UCVA and MR/BCVA as measured by ETDRS chart at 4m
- Concomitant Medications
- Ophthalmic Examination without dilation and with IOP
- Insert visualization
- Meibomian gland assessment (expressibility and quality)
- DED Assessment
 - Schirmer's
 - MMP9
 - Osmolarity
 - Conjunctival injection
 - TBUT
 - Ocular surface staining (sodium fluorescein and lissamine green)
- Subject reported AE's
- DEQ-5 

Week 12

- UCVA and MR/BCVA as measured by ETDRS chart at 4m
- Concomitant Medications
- Ophthalmic Examination without dilation and with IOP
- Insert visualization
- Meibomian gland assessment (expressibility and quality)
- DED Assessment
 - Schirmer's
 - MMP9
 - Osmolarity
 - Conjunctival injection
 - TBUT
 - Ocular surface staining (sodium fluorescein and lissamine green)
- Subject reported AE's
- DEQ-5 

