I. The investigator will use the NEI scale to grade the cornea using fluorescein and the conjunctiva using lissamine green at visits 1, 2, 3, 4, 5, 6.

II. The investigator will grade the level of ocular injection on a 0 to 4-point scale at visits 1, 2, 3, 4, 5, 6.

0 = None

1 = Mild – Slightly dilated blood vessels; color of vessels is typically pink; can be quadrantal

2 = Moderate – More apparent dilation of blood vessels; vessel color is more intense (redder); involves the majority of the vessel bed

3 = Severe – Numerous and obvious dilated blood vessels; in the absence of chemosis the color is deep red, may be less red or pink in presence of chemosis, is not quadrantic

4 = Extremely Severe – Large, numerous, dilated blood vessels characterized by unusually severe deep red color, regardless of grade of chemosis, which involves the entire vessel bed

III. The investigator will evaluate the expressibility and quality of the meibomian glands at visits 1, 2, 3, 4, 5, 6..

Grade scale for meibomian gland dysfunction		
Grade Scale	Percentage of blocked glands	Quality of meibomian secretion
Grade 1	40% - 50%	Clear to mild milky secretion
Grade 2	50% - 70%	Milky to pasty secretion
Grade 3	70% - 85%	Thick, pasty to very little secretion
Grade 4	85% - 90%	Very little to no secretion

IV. The investigator will use the InflammaDry to detect levels of MMP9 at visits 1, 2, 3, 4, 5, 6.

[figure not shown]

InflammaDry

[name] STUDY V1

V. The investigator will use Tear Lab to assess tear osmolarity at visits 1,2, 3, 4, 5, 6.

VI. The investigator will fill out the following questionnaire on the day of DEXTENZA® insertion (Screening visit):

Physician Ease of Insertion Questionnaire

The investigator will grade the level of ease of insertion of the intracanalicular insert on a 0 to 10-point scale.

The Investigator will record ease of insertion procedure on the appropriate Case Report Form.

0	1	2	3	4	5	6	7	8	9	10
---	---	---	---	---	---	---	---	---	---	----

Very Easy

Very Hard

VII. The investigator will have the patient complete the DEQ-5 questionnaire at visits 1,3,4,5,6,7.

DEQ-5

1. Questions about EYES DRYNESS:

a. During a typical day in the past month, how often did your eyes feel discomfort?

Never
 Rarely
 Sometimes
 Frequently
 Constantly

b. When your eyes feel discomfort, how intense was this feeling of discomfort at the end of the day, within two hours of going to bed?

Never have it Not at all intense Very intense

0
 1
 2
 3
 4
 5

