Although topical steroids have a limited role for chronic use in DED, they have been demonstrated to be of value in the short-term for refractory DED and for managing acute flares of DED. Studies have also demonstrated the value of topical steroids as an induction agent prior to initiating topical cyclosporine therapy. Cyclosporine 0.05%, while an effective topical immunomodulator agent, is associated with side effects upon instillation such as burning, stinging and conjunctival hyperemia. These side effects can discourage use of the topical agent and to promote improved adherence, prior work has described the short-term, adjuvant use of topical corticosteroids when starting cyclosporine 0.05% to mitigate the burning, stinging and other associated side effects. Furthermore, this combined approach has been shown to produce a faster response to therapy with a quicker improvement in signs and symptoms of dry eye.

Topical medication regimens, when used appropriately, can effectively manage ocular surface inflammation. However, drop adherence, complex medication regimens and difficulties with instillation are well-recognized challenges associated with topical therapies. In recent years,

notable innovation has occurred across ophthalmology as it relates to drug delivery to circumvent the known barriers associated with topical therapies. Recently, the dexamethasone ophthalmic insert (Dextenza 0.4 mg; Ocular Therapeutix) was introduced and was approved on-label for postoperative ocular inflammation and pain. The insert is a drug-eluting, intracanalicular plug that aims to provide a sustained and tapered release of steroid to the ocular surface over 30 days. In addition to studies reporting favorable results in patients after cataract surgery, a recent study by Ibach et al evaluated the insert in patients following PRK and reported that patients preferred the insert compared to topical steroids.

This present study aims to evaluate the use of adjunctive dexamethasone (in the form of the insert) in patients started on cyclosporine 0.05% (Restasis) for the treatment of dry eye disease. To the best of our knowledge, no prior studies have evaluated the use of the insert to manage ocular surface inflammation in DED.

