### **Main Outcome Measures**

The primary outcome measure was the mean change in corneal surface staining (guided by use of fluorescein and lissamine green) at weeks 1, 2, 4, 8 and 12 based on the NEI grading scale. Corneal fluorescein staining was graded from 0 to 3 (none to heavy) in five regions of the cornea and summed for a total score.

All secondary outcome measures followed the same timeline with comparison at weeks 1, 2, 4, 8 and 12 in comparison to baseline. Secondary outcome measures included the mean change in tear break-up time (TBUT), the mean change in conjunctival staining (graded 0-3 in 6 regions), the mean change in tear osmolarity as measured by TearLab, the mean change in DEQ-5, the mean change in meibomian gland scores as measured by quality of meibum expression, the mean change in best-corrected distance visual acuity (BCDVA) as measured by ETDRS chart and the mean change in Schirmer's score as measured by a Schirmer's test strip.

Meibomian gland scoring involved grading the quality of expression (0-3) from 15 glands along the lower eyelid including temporal, central and nasal. For scoring, 3 was representative of clear, liquid secretions and 0 was no secretions. The DEQ-5 Dry Eye Questionnaire was used to evaluate symptoms and characterize severity of discomfort, dryness and tearing. Possible scores ranged from 0 to 22 with higher scores representing worse symptoms.

On the screening visit and the initiation of therapy including implantation of the dexamethasone insert in the study group, a physician ease of insertion questionnaire was also completed by the physician implanting the device. All device-related complications were recorded. All subject-reported adverse events were recorded at each study visit.

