### **Statistical Analysis**

All statistical analysis was performed using Prism 9 software (GraphPad Software, Inc.). Repeated measures analysis of variance was performed to compare the values at each time point in each group. Post hoc analyses were also performed with Bonferroni correction to directly compare the mean values at each time point in comparison to baseline. A *P* value less than 0.05 was considered statistically significant.

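### Minor: conjunctival injection is graded before any study drop at baseline but at an uncontrolled time after a Restasis drop at weeks 1 to 12, so within-group change may include transient drop-related redness

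*Protocol*

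**What the plan says.** Protocol section 2.2 lists "Mean change in conjunctival injection from baseline at week 1, week 2, week 4, week 8 and week 12" as a secondary objective, graded 0 to 4 by the physician. Appendix item II gives the grading rule: "The investigator will grade the level of ocular injection on a 0 to 4-point scale at visits 1, 2, 3, 4, 5, 6". It then defines the five grades and says nothing about drops.

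Visit 1 is the screening/prescription visit. Section 5.1.1 has "Restasis BID OU prescription" there, so Restasis starts after that visit's assessments on the natural reading. Section 4.1.2 excludes "Patients who have been on topical immunomodulating agents in the previous 3 months to their baseline visit" and also patients on topical steroids. From then on, the synopsis puts all three groups on Restasis twice daily in both eyes for the 12 weeks; one group adds Lotemax twice daily for a month.

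Table 1 controls timing only through day windows. Section 4.3 adds that "patients may continue to receive all medications and standard treatments administered for other conditions". Neither these sections nor the appendices set a drop-free period or ask when the last drop was taken. The case report form is not among the documents.

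The SAP's Introduction states that cyclosporine 0.05% "is associated with side effects upon instillation such as burning, stinging and conjunctival hyperemia". Its Statistical Analysis section describes repeated-measures analysis within each group, with Bonferroni post hoc tests to "directly compare the mean values at each time point in comparison to baseline".

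**The concern.** The sign being graded is redness of the conjunctiva, and the SAP names conjunctival hyperemia on instillation as an effect of the drug that every patient takes. That source of redness is absent at baseline by design and possible at every later visit. In a comparison with baseline inside one group, it does not cancel.

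If some patients take the morning drop shortly before the examination, their grade reflects the drop as well as the disease. The group mean then looks less improved than it is, and variation in the interval between drop and examination adds noise. If no time of last drop is recorded, an analyst cannot identify or adjust for the affected visits afterwards. At stake is the reading of one secondary endpoint, if it is analysed.

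**Working it through.** The documents give no effect size, SD or power for injection, so there is no plan figure to reproduce. The check has two parts.

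**1. Does the chain hold in the text?**
- Baseline precedes any study drop: yes (sections 3.1, 4.1.2, 5.1.1).
- All eyes are on Restasis twice daily at weeks 1 to 12: yes (synopsis).
- The interval from drop to grading is controlled or recorded: no such instruction in sections 4.3, 5.1, 5.1.1 or the appendices.
- The drop can cause the graded sign: yes (SAP, Introduction), but with no frequency, grade or duration, and nothing on whether it persists to weeks 8 and 12.
- The described contrast is within group against baseline: yes (SAP, Statistical Analysis).

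**2. How large could it be?** Every input here is an assumption except the 10 patients per arm.
- Share of patients who react: 10% to 50%; added redness: one grade; duration: 0.25 h to 2 h.
- Last drop evenly spread over 0 to 8 h before the examination.
- Both eyes alike, so the patient is the unit; artefact independent of true change; SD of true change 0.5 to 1.0.

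Formulas: q = share reacting × duration / 8 h; mean shift = q × 1 grade; total SD = √(true SD² + q(1 − q)); SE = total SD / √10.

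| Case | q = shift (grade) | True SD | Total SD | SE | Shift / SE |
|---|---|---|---|---|---|
| Low: 0.10 × 0.25/8 | 0.003 | 1.0 | 1.002 | 0.317 | 0.01 |
| High: 0.50 × 2/8 | 0.125 | 1.0 | 1.053 | 0.333 | 0.38 |
| High | 0.125 | 0.5 | 0.599 | 0.190 | 0.66 |
| Extreme: 1.0 × 2/8 | 0.25 | 1.0 | 1.090 | 0.345 | 0.73 |
| Extreme | 0.25 | 0.5 | 0.661 | 0.209 | 1.20 |

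If the last drop is instead spread over 0 to 12 h, which twice-daily dosing also allows, the high case becomes 0.50 × 2/12 = 0.083 grade, or 0.46 SE at true SD 0.5.

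Effect on a within-group test, assuming a true improvement of 0.5 grade, SD 0.8, n = 10, two-sided 0.05 and a normal approximation:
- No artefact: SE = 0.8/√10 = 0.253; 0.5/0.253 − 1.960 = 0.016; power about 51%.
- Shift 0.125: 0.375/0.253 − 1.960 = −0.478; about 32%. Adding the artefact's variance, SD = √(0.64 + 0.109) = 0.866 and power is about 28%.
- Shift 0.25, the extreme case: 0.25/0.253 − 1.960 = −0.972; about 17%.
- Shift 0.003: practically unchanged.

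Direction: the expected artefact in the change equals study-drop redness at follow-up, plus non-study-drop redness at follow-up, minus non-study-drop redness at baseline. The first term cannot be negative. The other two need not balance.

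**The case against.** The opposing case is strong on consequence.

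- **No analysis is shown to be affected.** The SAP's list begins "Secondary outcome measures included the mean change in tear break-up time (TBUT), the mean change in conjunctival staining (graded 0-3 in 6 regions" and continues through osmolarity, DEQ-5, meibomian scores, acuity and Schirmer. Conjunctival staining is there; injection is not, and no injection results are given. This stands.
- **The protocol's question is comparative.** All arms take Restasis, so shared redness largely cancels between arms. This stands. A reader might infer that steroid use blunts the redness unequally and so biases the comparison of arms. The SAP speaks of topical steroids easing burning, stinging and other effects when cyclosporine is started, not of the insert, and it describes no between-arm test. Differential bias is possible but inferred.
- **The size is assumed.** One introductory sentence about tolerability supports the mechanism and nothing more. This stands. A fall in power from 51% to 17% would need every patient to react for two hours, so it should not be quoted as the expected loss.
- **The direction is not certain.** A reader might infer that the artefact can only mask improvement. That is true of study drops alone. Section 4.3 lets other medications continue, so other drops could redden the baseline grade too.
- **On-treatment redness may be the intended target.** The protocol does not say that drug-caused redness should be excluded, so this is partly a matter of choice. Even so, an uncontrolled interval since the last drop adds noise to either target.

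**Conclusion.** The point holds as a minor one, worth considering rather than required. The documents support every step up to a possible artefact: a baseline free of study drops, twice-daily Restasis afterwards, no control of the interval, hyperemia on instillation acknowledged, and a within-group contrast. They do not support a stated size. On the assumptions above, the shift is 0.003 to 0.125 grade, and most of that range is small against the sampling error of 10 patients.

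A reader might go further and blame drop timing for the failure to meet the primary endpoint. Nothing in the documents supports that: the primary endpoint is staining, the mechanism named is redness, and no link between them is given. No reported result is shown to be wrong. The recommendation rests on the low cost of the change and on the fact that, if no drop time was recorded, the artefact cannot be removed later.

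**What to change.** In section 5.1.1, tell patients in all arms to take the visit-day study drops (Restasis, and Lotemax where used) only after testing is complete. Record the clock time of the last drop with the concomitant-medication entry that Table 1 already has at every visit. Leave drops prescribed for other conditions unchanged, but record their time as well, including at baseline.

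The cost is one line of instruction and one recorded time per visit. Doses are delayed, not missed: Restasis 84 days × 2 = 168 doses per eye, with up to 5 delayed (5/168 = 3%); Lotemax, taking a month as 30 days, 30 × 2 = 60 doses, with up to 3 delayed at weeks 1, 2 and 4 (3/60 = 5%). For an afternoon visit the delay can be several hours.

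The SAP already reports completed work, so the instruction helps mainly if the protocol is reused. If injection data already collected are reported, state the uncontrolled drop timing as a limitation.

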## INTRODUCTION

Dry eye disease (DED) is a chronic, multifactorial disease process of the tear film and ocular surface associated with pain, discomfort and blurry vision with the potential to have a considerable impact on quality of life. The multifactorial and complex nature of DED was highlighted in the recently revised definition by the Tear Film and Ocular Surface Society's Dry Eye Workshop II in 2017 in which DED was defined as a "multifactorial disease of the ocular surface characterized by a loss of homeostasis of the tear film, accompanied by ocular symptoms in which tear film instability and hyperosmolarity, ocular surface inflammation and damage, and neurosensory abnormalities play etiological roles." As inflammation of the ocular surface is thought to be a core mechanism of DED, topical anti-inflammatory agents play a pivotal role in the management of DED.

The importance of addressing and minimizing ocular surface inflammation in the treatment of DED is well established. Multiple topical treatment options are available including topical corticosteroids and topical immunomodulators such as cyclosporine 0.05% and lifitegrast. Topical corticosteroids are effective at reducing and controlling ocular surface inflammation but long-term use carries the risk of cataract formation, increased intraocular pressure (IOP) and glaucoma. Cyclosporine and lifitegrast are both staples of the dry eye treatment armamentarium for long-term, local control of ocular surface inflammation. Cyclosporine 0.05%, which has been in use for nearly 20 years, has a well-established safety profile and has been shown to be efficacious in reducing ocular surface inflammation and increasing tear production.

Although topical steroids have a limited role for chronic use in DED, they have been demonstrated to be of value in the short-term for refractory DED and for managing acute flares of DED. Studies have also demonstrated the value of topical steroids as an induction agent prior to initiating topical cyclosporine therapy. Cyclosporine 0.05%, while an effective topical immunomodulator agent, is associated with side effects upon instillation such as burning, stinging and conjunctival hyperemia. These side effects can discourage use of the topical agent and to promote improved adherence, prior work has described the short-term, adjuvant use of topical corticosteroids when starting cyclosporine 0.05% to mitigate the burning, stinging and other associated side effects. Furthermore, this combined approach has been shown to produce a faster response to therapy with a quicker improvement in signs and symptoms of dry eye.

Topical medication regimens, when used appropriately, can effectively manage ocular surface inflammation. However, drop adherence, complex medication regimens and difficulties with instillation are well-recognized challenges associated with topical therapies. In recent years,

notable innovation has occurred across ophthalmology as it relates to drug delivery to circumvent the known barriers associated with topical therapies. Recently, the dexamethasone ophthalmic insert (Dextenza 0.4 mg; Ocular Therapeutix) was introduced and was approved on-label for postoperative ocular inflammation and pain. The insert is a drug-eluting, intracanalicular plug that aims to provide a sustained and tapered release of steroid to the ocular surface over 30 days. In addition to studies reporting favorable results in patients after cataract surgery, a recent study by Ibach et al evaluated the insert in patients following PRK and reported that patients preferred the insert compared to topical steroids.

This present study aims to evaluate the use of adjunctive dexamethasone (in the form of the insert) in patients started on cyclosporine 0.05% (Restasis) for the treatment of dry eye disease. To the best of our knowledge, no prior studies have evaluated the use of the insert to manage ocular surface inflammation in DED.

## Methods

This was a prospective, open-label, interventional study performed at a single site (Cleveland, OH). This study was conducted in compliance with the Declaration of Helsinki and was reviewed and approved by the Salus Institutional Board IRB on August 12, 2020. All participants provided written informed consent.

## Patients

60 eyes of 30 patients age  $\geq 18$  with clinically diagnosed aqueous-deficient dry eye disease and determined to be a candidate (based on clinical judgment) for treatment with a topical immunomodulator were enrolled in the study.

Patients were excluded if they had been on topical immunomodulation therapy in the 3 months prior to screening, were actively being treated with topical, oral or intravenous immunosuppressive agents, had a hypersensitivity to dexamethasone, had active infectious systemic or ocular disease or had altered nasolacrimal flow of either acquired or congenital origin. Pregnant patients were also excluded.

Following screening and informed consent, patients were randomized into 3 groups; a study group and 2 control groups. Each group included 10 patients. The study group was started on cyclosporine 0.05% and was implanted with an intracanalicular, 0.4 mg dexamethasone insert in both eyes. The first control group was started on cyclosporine 0.05% in conjunction with topical loteprednol 0.5% twice daily. The 2nd control group was started on cyclosporine 0.05% as monotherapy.

The study period lasted 12 weeks including one screening/prescription visit and follow-up visits which occurred at weeks 1, 2, 4, 8 and 12 following initiation of therapy. At weeks 1, 2, 4, 8 and 12 the primary and secondary endpoints were assessed.

